Official Study Title: Capsaicin 8% Patch for Spinal Cord Injury Neuropathic Pain

NCT number: NCT02441660

IRB Approval Date: 07.24.2019

Unique Protocol ID: HSC20150322H

Protocol Template Form

Item 1 UTHSCSA	15-322H
Tracking Number	

Item 2 Abstract / Project Summary

Provide a succinct and accurate description of the proposed research. State the purpose/aims. Describe concisely the research design and methods for achieving the stated goals. This section should be understandable to all members of the IRB, scientific and non-scientific.

DO NOT EXCEED THE SPACE PROVIDED.

Purpose/Objectives: Current pharmacologic agents for neuropathic pain (NP) in Spinal Cord Injury (SCI) provide 20-30% pain reduction at best; so there is clear need for research studies on new promising evidence-based therapeutic agents. Animal spinal cord injury models show the Transient Receptor Potential Vanilloid subfamily, member 1 (TRPV1) defunctionalization with capsaicin decreases nociceptor hyperactivity. Human trials are needed to substantiate this effect. Most systemic effects of oral agents often limit tolerability, especially as doses are titrated up to achieved maximum clinical effect. Analgesics that can be applied topically have the potential to largely overcome this problem; the only published study of a topical analgesic in persons with SCI examined low dose capsaicin cream in 8 SCI persons and found efficacy. Thus more studies on topical analgesics are needed in persons with SCI. We propose to conduct the first prospective trial of Capsaicin 8% (C8P) in persons with SCI, with hopes to provide SCI patients and clinicians with evidence for a much-needed alternative topical therapeutic without the systemic effects that often limit tolerability.

Research Design/Plan: Randomized dual balanced 2-sequence 2-treatment, 2-period (each period is 12 weeks long), crossover study; with an additional prospective trial arm

Methods:

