RCT: Pre-study data including subjective description of pain, baseline VAS, LANNS and NPRS. Pre-study data collection will include an intake form with subjective description of pain, baseline VAS / LANNS/NPRS, a numerical scale such as SF36 that measures quality of life parameters, subjective FIM scores, and pain diagrams will be obtained on each participant via the outpatient spinal cord injury clinic, or inpatient spinal cord injury unit.

Substudy: Non randomized, non-controlled arm: no pre-study data collection.

RANDOMIZATION: (RCT only)

Randomized dual balanced 2-sequence 2-treatment, 3-period, crossover study (see Table 1).

Tale 1. The proposed study layout

	Period	
Sequence	1	2
1	Α	В
2	В	Α

Where A indicates 8% Capsaicin and B indicates Low dose capsaicin control patch [1]. Each treatment period will be 12 weeks in duration. The proposed design is a standard 2-period, 2-treatment, 2-sequence design. Inclusion criteria: >1year post SCI, chronic neuropathic pain with VAS>3, pain below the level of injury and failure of at least 3 oral or topical pharmacological agents. Exclusion criteria: painful area >1120cm² (4 patches), skin breakdown over area and uncontrolled hypertension.

Methods:

RCT: Each participant will be randomized to one of two sequences:

Sequence 1: C8P application followed by one reapplication of a low dose capsaicin control patch (0.025% Well Patch) (available over the counter)

ÒR

Sequence 2: Control patch (0.025% Well Patch) followed by one replication of C8P, as indicated in Table 1.

Patch application method: Per manufacturers' application directions, the painful area will be treated with topical lidocaine

2.5%/prilocaine 2.5% for 1 hour prior to application of the test patch(es). Active and control patches will then be applied and left in place for one hour. After removal, the cooling gel will be applied to decrease any burning sensation from the capsaicin, per manufacturers' protocol. Blood pressure will be monitored every 30minutes after the capsaicin (control or treatment) patch over the hour of application.

Substudy: Non-randomized, non-controlled prospective arm: Patients with SCI undergoing patch as routine medical treatment for refractory neuropathic pain will be recruited and enrolled immediately after patch application. Subsequently, they will be followed for a 12 week period using the identical protocol of data collection post patch application in the RCT, without reapplication of a control patch.

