Post patch application data collection (RCT and substudy): Measurements of the primary outcome (VAS) will occur every 2 weeks and all secondary outcomes will be measured at 4, 8 and 12 weeks within each period in each sequence. Every 2 week VAS scores will be collected via phone at weeks 2,6,10 and in person at weeks 4, 8, 12. All secondary outcomes surveys will be done at a face to face visit at weeks 4, 8, 12.

Outcome measures: (RCT and substudy)

: Primary efficacy endpoint is the visual analog scale (VAS) score at the end of each of the three 12-week periods (at weeks 12 and 24). Secondary outcome measures include the Multidimensional Pain Inventory (MPI) Pain Severity Subscale, MPI-SCI, International SCI Pain Basic Data Subset (SCIPBDS), WHOQOL-BREF, Spinal Cord Independence Measure (SCIM) and number of concomitant pain medications

Specific Aims

- 1. Determine the effect of the capsaicin 8% patch on VAS scores.
- 2. Determine the effect of the 8% Capsaicin (C8P) on QOL.
- 3. Determine the effect of the C8P on physical function. .

UHS clinic sites: Patients will be approached by providers (who are also investigators in this study), regarding being contacted by phone to hear more about the study. If agreeable patient's name and phone number will be provided manually/verbally to the study team at the VA in order to contact interested patients. No PHI will be transferred electronically between UHS and the VA. Data for the study will be provided by patient and collected at the VA.

Data Analysis Plan:

RCT: Due to the small population of individuals with a spinal cord injury and high incidence of neuropathic pain in such persons and lack of prospective studies on the capsaicin 8% patch, we felt a small group of 25 patients was large enough to show possible potential benefits, small enough to realistically complete this study, follow patients appropriately according to standard of care, and in congruence with the small population size commonly seen in spinal cord injury studies. This study will serve as pilot data for a larger study in the future.

Substudy: Non-randomized, non-controlled arm: 50 participants will be enrolled and we will use the baseline and post patch application data to help determine the number needed to treat and minimal clinically important difference for the RCT.

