RCT and substudy: Data analysis will be performed on subjective description of pain at baseline from NPRS, VAS and evaluated at 2, 4, 8, 12 weeks post application to determine efficacy of capsaicin 8% patch in regards to point value and percentage of reduction compared to baseline. Longevity as recorded by reduction in baseline NPRS and VAS scores in days, weeks, and months of relief until pain returns to baseline. We will also compare our quality of life scale (WHO-QOL) and SCIM scores from pre study to post study and evaluate for more subjective measures of improvement in quality of life and functional improvement respectively. In the RCT trial we will assess for significant differences is outcomes between the treatment and control groups over time whereas, in the non-randomized, non-controlled trial we will compare baseline scores to 12 weeks post patch application scores for all outcomes. The significance of variation in the mean outcome with treatment will be assessed with a mixed effects linear model of the outcome in terms of sequence, subject nested in sequence, period, treatment, and first order carryover. All statistical testing will be two-sided with a significance level of 5%. SAS Version 9.4 for Windows or later, SAS Instititue, Cary, North Carolina, or R will be used throughout.

0

15-322H, [name], Form BC, 07-24-19, AMD.docx vSept3-2014

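### The RCT model includes a carryover term that the two-period AB/BA layout cannot estimate, so it gives no carryover-adjusted treatment test; the term should be dropped and the assumption stated

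*Combined protocol and SAP*

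**What the plan says.** The Data Analysis Plan in Item 6 states: "The significance of variation in the mean outcome with treatment will be assessed with a mixed effects linear model". The terms are given as a "mixed effects linear model of the outcome in terms of sequence, subject nested in sequence, period, treatment, and first order carryover". The same paragraph adds: "All statistical testing will be two-sided with a significance level of 5"%. It does not say whether tests are sequential or partial, or what happens if a term is redundant. The other analyses mentioned there (change from baseline, duration of relief, group differences over time) name no model.

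On the layout, the abstract (Item 2) has a "Randomized dual balanced 2-sequence 2-treatment, 2-period (each period is 12 weeks long), crossover study". Table 1 in Item 6 shows the sequences AB and BA, and the text after it says: "The proposed design is a standard 2-period, 2-treatment, 2-sequence design". Two phrases differ. The Randomization section opens with "Randomized dual balanced 2-sequence 2-treatment, 3-period, crossover study (see Table 1", and Outcome measures places the primary endpoint "at the end of each of the three 12-week periods (at weeks 12 and 24", which is three periods with two time points.

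The RCT collects "Pre-study data including subjective description of pain, baseline VAS, LANNS and NPRS" before treatment. On duration of effect, Item 4 hopes for 8 to 12 weeks of relief from one application. Item 3 cites a retrospective review of three patients with an average of 169 days. No washout is stated.

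**The concern.** In a two-period, two-sequence crossover, first-order carryover cannot be separated from the sequence and treatment effects. A plan that lists all three promises a treatment effect adjusted for carryover, which the layout cannot supply. A reader of the results would reasonably believe that the adjustment had been made.

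At stake is what the reported treatment difference means. The usual estimate rests on there being no carryover difference between the two patches, and the plan never states that assumption. The period count belongs to the same point, because a third period could make the listed terms estimable.

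**Working it through.** The plan gives no degrees of freedom, power, SD or effect size to reproduce. The 25 RCT patients are justified by feasibility and pilot status.

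**1. Rank.** The coding follows Table 1, with C8P = +1 and control = -1, and carryover 0 in period 1.

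| Cell | Sequence | Period | Treatment | Carryover |
|---|---|---|---|---|
| AB, period 1 | 1 | -1 | 1 | 0 |
| AB, period 2 | 1 | 1 | -1 | 1 |
| BA, period 1 | -1 | -1 | -1 | 0 |
| BA, period 2 | -1 | 1 | 1 | -1 |

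Row by row, (sequence - treatment)/2 = 0, 1, 0, -1, which is the carryover column. With the intercept there are five columns of rank 4. Removing treatment also leaves rank 4, so treatment adjusted for all listed terms has 4 - 4 = 0 df. Sequence and carryover likewise have 0, and period has 1.

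**2. Subject effects.** With 25 patients and two values each there are 50 observations. Sequential df in the listed order are sequence 1, subject 23, period 1, treatment 1, carryover 0. With the intercept the total rank is 27, leaving 50 - 27 = 23 residual df. If carryover were entered before treatment, the 1 df would go to carryover and treatment would have 0.

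**3. Repeated visits.** Using all six two-weekly VAS values per period, with a visit effect, gives rank 9 of 10. The alias remains.

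**4. What the usual estimate measures.** Let t be the C8P-minus-control effect and L the C8P-minus-control carryover into period 2. The mean period-1-minus-period-2 difference is p + t - L(A) in sequence AB and p - t - L(B) in sequence BA, where p is the period difference. Half the difference between the two is t - L/2. If relief persists, L has the sign of t and the estimate is smaller in size than t as long as L/t is below 4. Its sign reverses once L/t exceeds 2.

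**5. Precision.** Assumptions: a 12/13 split, no dropout, and one correlation r between any two VAS measurements. 1/12 + 1/13 = 0.1603. SEs are in units of the VAS SD.

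| | Formula | r = 0.3 | r = 0.5 | r = 0.7 |
|---|---|---|---|---|
| Crossover, no carryover term | sqrt[(1-r)/2 × 0.1603] | 0.237 | 0.200 | 0.155 |
| Period 1, unadjusted | sqrt[0.1603] | 0.400 | 0.400 | 0.400 |
| Period 1, adjusted for baseline VAS | sqrt[(1-r²) × 0.1603] | 0.382 | 0.347 | 0.286 |
| Adjusted period 1 / crossover | ratio | 1.6 | 1.7 | 1.8 |
| Break-even carryover L | 2 sqrt[SE(period 1, adjusted)² - SE(crossover)²] | 0.60 | 0.57 | 0.48 |

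Below the break-even L, the crossover estimate has the smaller mean squared error. Keeping carryover and dropping the fixed sequence term, with subjects random, reproduces the unadjusted period-1 row. A 10/15 split changes little: crossover 0.242/0.204/0.158, adjusted period 1 0.389/0.354/0.292.

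**6. Timing.** In sequence AB, C8P is applied at day 0, and the period-2 endpoint at week 24 is day 168. Relief of 8 to 12 weeks ends between days 56 and 84, at or before the start of period 2. An average of 169 days reaches just past day 168. Visits early in period 2 are more exposed than week 24.

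**The case against.** The strongest reply is that nothing breaks in practice. The plan does not call for partial tests. In the listed order treatment has 1 df, and a program that discards the last redundant column reports the standard within-patient estimate. That is correct. A reader might infer that the RCT treatment test cannot be computed at all, but the documents do not support this. Only the test adjusted for both sequence and carryover is unavailable. What survives the reply is that the written model claims an adjustment it does not make.

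A second reply is that entering baseline VAS as an additional response makes every listed term estimable (rank 6 of 6). The plan does not say this: the primary endpoint is VAS at weeks 12 and 24, and baseline serves as the reference for reduction. The SE would be 0.474/0.400/0.310 SD at the three correlations, twice the crossover SE and worse than the baseline-adjusted period-1 comparison. Using baseline as a covariate or in change scores does not break the alias.

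Third, the two mentions of three periods could suggest a three-period design, in which the terms can be estimable. The documents describe no third period: one mention points to Table 1, the other lists only weeks 12 and 24, and each sequence has two applications. They read as wording errors.

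Fourth, this is a 25-patient pilot with no power claim, and persisting relief would more likely hide an effect than create one. Both points lower the severity. They do not remove the need to define an estimate that is meant to inform a larger study.

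**Conclusion.** The model is wrong as written and should be corrected, but the fault is one of specification and does not invalidate the trial. The rank result (4 of 5, carryover = (sequence - treatment)/2) is exact for Table 1 and needs no assumption. The likely default analysis is sound if there is no differential carryover; otherwise it is off by half the carryover difference, towards no difference when C8P relief persists (unless that carryover exceeds four times the effect).

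It would go too far to conclude that carryover will distort the week-24 result. The 8-to-12-week figure argues against it, and the only contrary evidence is an average over three patients.

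The SEs, ratios and break-evens rest on the assumed correlations, split and absence of dropout. The adjusted period-1 formula is a large-sample one and slightly optimistic at this size. The entry requirement of VAS above 3 may also weaken the baseline correlation. These figures help choose between estimators and are not evidence of the fault.

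**What to change.** 1. Reconcile the two three-period phrases (Randomization and Outcome measures, Item 6) with Table 1, the two-period statements in Items 2 and 6, and the week 12 and 24 endpoints. A three-period model needs consideration only if the sponsor confirms a third period.
2. Delete the carryover term and name the primary model. Suggested text: *The primary analysis is a linear mixed model of week-12 VAS in each period, with fixed effects for treatment, period and sequence and a random effect for subject within sequence. The C8P-minus-control difference is reported with its 95% confidence interval. The same fixed-effect structure is used for the secondary outcomes.* Say also how visits enter the comparison over time.
3. State the assumption. Suggested text: *This assumes no differential carryover. Otherwise the expected estimate is the true effect minus half the carryover difference, so persisting C8P relief would bias it towards no difference.* Discuss it against both durations in Items 3 and 4, and against the trial's own sequence-1 week-12 VAS relative to baseline, which shows whether relief is still present when period 2 begins.
4. Add a sensitivity analysis: *Period-1 week-12 VAS is compared between sequences, adjusted for baseline VAS.*

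The cost is a text amendment, with no new visits or data. The downside is that the assumption becomes explicit and must be defended, and that the sensitivity estimate is markedly less precise than the primary one.

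### The RCT model omits the pre-study VAS that the RCT collects; this loses precision in between-patient comparisons only, and sequence and carryover must be separated before the gain can be had

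*Combined protocol and SAP*

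**What the plan says.** - **Baseline.** Item 6, pre-study data collection, has for the RCT: "Pre-study data including subjective description of pain, baseline VAS, LANNS and NPRS". Item 2 also lists a baseline VAS. The substudy has none ("Substudy: Non randomized, non-controlled arm: no pre-study data collection"), so the point concerns the RCT only.
- **Layout.** Table 1 is AB/BA, and Item 6 says: "The proposed design is a standard 2-period, 2-treatment, 2-sequence design". Also: "Each treatment period will be 12 weeks in duration". No washout or second baseline is described. Elsewhere Item 6 speaks of three periods, once in the randomization text and once in the endpoint definition, although the latter names only weeks 12 and 24.
- **Endpoint and model.** The primary endpoint is the VAS score at the end of each period. The Data Analysis Plan tests treatment with a "mixed effects linear model of the outcome in terms of sequence, subject nested in sequence, period, treatment, and first order carryover". It does not say whether the outcome there is the score or the change.
- **Use of baseline.** The same section uses baseline for "point value and percentage of reduction compared to baseline", for how long relief lasts until pain returns to baseline, and for pre-to-post comparison of quality of life and function. None of these puts it in the model.
- **Size.** The RCT has 25 patients, justified by feasibility: "we felt a small group of 25 patients was large enough to show possible potential benefits". No SD, correlation, power or dropout rate is given.

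**The concern.** A pre-study score often explains part of the spread between patients in a later score, and leaving it out of the model leaves that spread in the error. In a crossover this matters only where patients are compared with other patients.

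This plan asks for such a comparison, because it wants treatment adjusted for first-order carryover. Carryover is a live question on the document's own figures: Item 4 hopes for 8-12 weeks of relief from one application, and the three-patient review in Item 3 reports an average of 169 days, against a period of 12 × 7 = 84 days. In AB/BA the carryover-free treatment effect rests on period 1 alone, about 13 patients against 12. There a chance difference in starting pain passes into the treatment effect in proportion to the baseline-to-endpoint correlation.

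**Working it through.** The plan has no power or precision figure to reproduce, so the check starts from the design.

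**Inputs from the documents:** 25 patients; AB/BA; one pre-study VAS per patient; the listed model terms.

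**Assumed:** 13 and 12 patients per sequence; endpoint SD = 1; baseline-to-endpoint correlation r = 0.2 to 0.6; within-patient correlation between periods ρ = 0.5 to 0.7; 4 to 8 patients with period 1 only.

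**1. Is the stated model estimable?** AB/BA has four sequence-by-period means. Intercept, sequence, period, treatment and carryover are five parameters. Code sequence and treatment as ±1, and carryover as 0 in period 1 and the previous treatment in period 2. In every cell carryover = (sequence − treatment)/2. The rank is 4 of 5, and the treatment effect is not estimable. With baseline added, the rank is 5 of 6 and it is still not estimable.

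**2. The carryover-adjusted effect with sequence dropped.** Four parameters then fit four means, and the treatment effect is the period-1 difference between sequences.
- Variance = 1/13 + 1/12 = 0.1603; SE = 0.400 SD.
- Difference detectable with 80% power (two-sided 5%, normal approximation) = (1.96 + 0.84) × 0.400 = 1.12 SD.
- The chance difference in mean baseline has the same SE, 0.400 baseline SD. At r = 0.5 it shifts the contrast by 0.5 × 0.400 = 0.20 SD for a one-SE imbalance.

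**3. The same effect with baseline as covariate.** Estimating the slope from 25 patients costs a factor of 22/21, so the variance ratio is (1 − r²) × 22/21.

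| r | Variance ratio | SE (SD) | Detectable at 80% (SD) |
|---|---|---|---|
| 0.2 | 1.006 | 0.40 | 1.12 |
| 0.3 | 0.953 | 0.39 | 1.09 |
| 0.4 | 0.880 | 0.38 | 1.05 |
| 0.5 | 0.786 | 0.35 | 0.99 |
| 0.6 | 0.670 | 0.33 | 0.92 |

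Simulation of the period-1 analysis gave 0.89, 0.78 and 0.67 at r = 0.4, 0.5 and 0.6. The break-even is r = √(1/22) = 0.21.

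**4. Change from baseline instead of adjustment.** With equal baseline and endpoint variances, the change-score variance relative to the adjusted variance is 2(1 − r) / [(1 − r²) × 22/21]. This is 1.36, 1.27 and 1.19 at r = 0.4, 0.5 and 0.6. Simulation gave 1.37, 1.27 and 1.20. So change scores carry about 20-37% more variance.

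**5. The carryover (sequence) test.** It compares patient means over both periods. Baseline multiplies its variance by [1 − 2r²/(1 + ρ)] × 22/21. At r = 0.5 and ρ = 0.6 this is [1 − 0.5/1.6] × 22/21 = 0.72.

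**6. The main within-patient contrast (sequence, period, treatment, no carryover; subject random).**
- Complete pairs: variance ratio 1.000. The pre-study value is the same in both periods and cancels.
- 4 of 25 patients with period 1 only: 0.996 to 0.978 for r = 0.4-0.6 and ρ = 0.5-0.7.
- 8 of 25: 0.993 to 0.955.

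So the gain from one-period patients is roughly 0.5-5% of variance. If subject were fitted as fixed it would be nil: baseline is absorbed by subject, and one-period patients add nothing to the treatment contrast.

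**The case against.** **The carryover-adjusted gain belongs to a model the plan does not specify.** This stands. A reader might infer that the stated model merely estimates the carryover-adjusted effect imprecisely, and that one added covariate recovers the loss. Step 1 rules that out: the effect is not identified, with or without baseline. The gain in step 3 appears only once sequence is dropped or period 1 is analysed by itself. If carryover is dropped instead, complete pairs gain nothing for treatment.

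**The main comparison is not weakened.** A reader might infer that the omission harms the crossover comparison in general. It does not. With complete pairs and no carryover term, leaving baseline out costs the treatment effect nothing.

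**The three-period wording could change the answer.** Under an assumed ABB/BAA layout the stated model is full rank, and baseline changes nothing with complete data (variance 0.0300 with and without it, at ρ = 0.5). But the documents give no three-period layout. Table 1, the sentence calling the design two-period, and the week 12 and 24 endpoints all describe two. The wording must be reconciled, but it does not remove the point for the layout shown.

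**The correlation is unknown, and entry at VAS>3 may lower it.** This stands. The precision is not free at every value of r.

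**The comparison with change scores may not apply,** since the endpoint is defined as the score. It matters only because the analysis text leaves the model outcome open.

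**Conclusion.** The point holds in a bounded form. The RCT collects a pre-study VAS and its model does not use it. In the AB/BA layout that loses precision in the between-patient quantities and in nothing else.

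- **Period-1 treatment effect:** variance about 12%, 21% and 33% lower with adjustment at r = 0.4, 0.5 and 0.6; about 5% lower at 0.3; no gain at 0.2.
- **Carryover test:** a gain of similar order.
- **One-period patients:** a small gain, roughly 0.5-5% of variance if 4-8 of 25 give period 1 only.
- **Complete pairs:** none.

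The aliasing of sequence and carryover is the more basic fault and has to be settled first. These sizes rest on assumed correlations, a 13/12 split, and two periods. The change is worth making because the data are already planned and because it fixes the choice between score, change and adjusted score in advance, in a 25-patient trial meant as pilot data for a larger one.

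**What to change.** 1. Do not fit sequence and carryover together. Make sequence, period and treatment, with subject random, the main model. Report the carryover-free effect as a period-1 comparison (equivalently, keep carryover and drop sequence).
2. Add pre-study VAS as a prespecified fixed covariate in both analyses. Do the same with the matching pre-study score for each secondary outcome that has one. Items 2 and 6 list different pre-study instruments for quality of life and function (WHOQOL-BREF and SCIM against SF36 and FIM), so first settle which are collected.
3. State that the model outcome is the VAS score in points, with point or percent reduction from baseline as description only.
4. Reconcile the three-period wording in the randomization and endpoint text with Table 1.

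**Cost:** a few lines in the analysis plan and no new data for the VAS analysis. The covariate uses one between-patient degree of freedom, leaves the complete-pair treatment contrast unchanged, and loses slightly in the period-1 comparison if r is below about 0.2 (ratio 22/21 = 1.05 at r = 0).
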